## 6. Trial treatment

#### 6.1 IMP details

The investigational medicinal products (IMPs) for this study, where licensed drugs, will be sourced from local hospital stock within the participating centres.

#### 6.2 Treatment details

Refer to the IMP-specific appendices for details.

#### **6.3 Concomitant treatments**

Participants may remain on a stable dose of riluzole, refer to section 4, (as a NICE standard of care) throughout the duration of the trial but are encouraged not to initiate or stop riluzole for the duration of the trial. In the event that changes are made to riluzole treatment during the trial, this will be documented in the eCRF.

The following medications are contraindicated with study treatment:

- Use of the allocated EXPERTS-ALS study drug, either for their licenced indications or off-label, or drug in the same class.
- Use of any medications post-randomisation that are contraindicated with the allocated study drug (refer to IMP-specific appendices).

In the event that a contraindicated medication is required by a participant, a medical assessment should be completed urgently and the study drug withheld. If a patient requires the ongoing use of a contraindicated medication the study drug should be discontinued, however every effort should be made to follow up the participant as per protocol. If the contraindicated drug is only required for a short period then the patient may re-commence the study drug once the contraindicated medicine is stopped according to the investigator's discretion.

There may also be medications which should only be used with caution as detailed in SmPC section 4.5. If a participant requires the use of any of these medications they may continue the study drug at the investigators discretion with additional monitoring as decided by the site PI as necessary.

#### 6.4 Dispensing

IMPs will be dispensed from local hospital stock and the study does not mandate the use of a specific brand of each IMP. Trial-specific dispensing and labelling will be required. Participants will be dispensed a sufficient supply of medication to last until their next

scheduled study visit. Prescribing and dispensing may be completed in advance of a study visit if required provided the study team has contacted the participant in advance of writing the prescription to determine the appropriate dose and quantity required. Further details are provided in the Pharmacy Manual and Research Manual. Where necessary, and in accordance with local policies, study drugs may be delivered to the participant by the research team or couriered to participant homes. Unused IMP and used, unused and part-used packaging will be returned at the next study visit to allow compliance and accountability checks to be completed. Local destruction policies will be followed. Full dispensing details will be provided in a study-specific pharmacy manual.

#### 6.5 Accountability

Master accountability logs will not be mandated and ring-fencing is not required. However, sites may choose to do this locally to manage supplies. Participant-level IMP accountability documentation will be maintained by clinical trials pharmacy. Local records and procedures can be used provided these allow patient level batch numbers and quantities to be matched to participants and archived. Otherwise, additional trial-specific records will be required where local processes are not sufficient. Full details will be provided in a study-specific pharmacy manual.

#### 6.6 Adherence

Participants will be asked about adherence at each study visit and their responses recorded in the eCRF. Participants will also be asked to return all used, unused and part-used packaging to allow adherence to be assessed where possible. Refer to the study-specific Research Manual and Pharmacy Manual for more details.

#### 6.7 Dose Modification and interruptions

In the case of adverse events felt to be clinically significant and related to study treatment by the local investigator, the IMP may be withheld, interrupted or discontinued or the dose may be reduced at the investigator's discretion in the interests of the participant. The adverse event(s) and dose modification / interruption will be documented in the study records. Refer to section 9.10 for more details on early discontinuation of study treatment.

Refer to the IMP-specific appendices for guidance on missed doses, and treatment interruptions.

#### 6.8 Overdose

Participants will be counselled on the importance of taking the study medications as prescribed. An overdose is defined as taking double the normal medication/day for one day or more. In the event that an overdose of study medication occurs, the participant will contact the local EXPERTS-ALS study team as soon as possible to receive appropriate advice. Participants will be provided with an out of hours contact number but will be advised to attend A&E in the case of an emergency. Participants will then be managed on a case-by-case basis and toxicity will be managed according to standard practice. An overdose leading to an SAE should be managed clinically and the procedures in Section 10 should also be followed. Overdoses will be documented.

## 7. Randomisation and enrolment

Prior to randomisation, all screening investigations will be reviewed by the local medically qualified investigator to confirm eligibility. The investigator will complete and sign the "Confirmation of Eligibility" form as documentation of this review. The investigator will be

responsible for indicating which of the treatment arms the patient is eligible for as this information will be required for randomisation. A patient must be eligible for a minimum of two treatment arms.

Once eligibility has been confirmed and baseline data recorded, the participant will be randomly allocated to one of the current treatment options for which they are eligible. A member of the local study team will perform the randomisation by accessing a web-based randomisation system provided by the Sheffield CTRU (SCRAM). Patient details (ID, age, eligibility details) will be entered and the treatment allocation will be returned. We will use probabilistic minimisation to balance site of onset (bulbar vs spinal) and groups of trial sites based on patient volume (high (Oxford, Sheffield, King's College) vs medium (Salford, University College London, Newcastle, Liverpool) vs low (Cambridge, Edinburgh, South Wales, Exeter)).

Following randomisation, all patients must be given a patient contact card. Site on-call contact details for 24-hour medical care must be added to this card, and participants advised to carry this with them at all times whilst participating in the trial. Where licenced products, 24-hour medical care will be provided via routine out of hours services i.e. trial-specific out of hours cover will not be required. Where non-licenced products, please refer to the IMP-specific appendices for more information.

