#### Figure 1: Illustration of analyses and adaptations at trial arm level

#### Figure 2: Illustration of potential adaptations at trial level following futility analyses.

#### No drug retained aft

#### Futility analysis 1

- The three futile drugs are dropped from the trial.
- Three new drugs are included.
- Recruitment proceeds for new drugs at least until futility analysis 1 of the next cycle.

#### Futility analysis 2

- The three futile drugs are dropped from the trial.
- Three new drugs are included.
- Recruitment proceeds for new drugs at least until futility analysis 1 of the next cycle.

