If a concurrently randomised candidate drug was not declared futile based on arm-specific Bayesian predictive probabilities obtained in futility analyses 1 and 2, we will estimate pairwise between-group mean differences in NFL levels at 18 to 24 weeks with 95% credible intervals and Bayesian posterior probabilities of non-inferiority, and, if reached, superiority to the reference drug after 80 patients per arm reached 24 weeks of follow-up. Drugs that were dropped due to futility after futility analysis 1 or 2 will not be included in non-inferiority or superiority analyses.

Irrespective of which conclusion was reached for a drug, we will estimate arm-specific mean changes from baseline with 95% credible intervals with final posterior probabilities to reach a reduction from baseline. Using Bayesian network meta-analysis, which fully maintains

concurrently randomised comparisons, we will then rank all candidate drugs by their effectiveness in decreasing NFL levels and calculate the posterior probability that each candidate drug has the highest or lowest NFL decrease from baseline.

Candidate drugs associated with a decrease in NFL levels will become candidates for investigation in a Phase III trial, particularly if they were considered non-inferior or superior to effective reference drugs as described above. Candidate drugs that ranked lower than reference drugs but were associated with a decrease in NFL levels can be considered for investigation in a Phase III trial based on other possible advantages, such as better safety profile and/or lower costs.

The first candidate drug that is retained after futility analyses 1 and 2 and associated with >97.5% probability of a reduction in mean group NFL levels different from zero at 18 to 24 weeks after 80 patients per arm reached 24 weeks of follow-up will be considered the first reference drug. As the trial continues, patients will continue to be randomised to this reference drug as long as DMEC and/or TMG do not consider another candidate drug as reference. Figure 2 (above) illustrates potential adaptations to trial arms following the planned futility analyses for the example of three concurrently evaluated drugs.

Candidate drugs should be considered as the potential new reference drug by the DMEC and/or TMG under two scenarios:

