#### **Exclusion criteria**

Pre-existing diabetes is an exclusion for the metformin arm in this study.

Other exclusions are as per the SmPC:

- Hypersensitivity to metformin hydrochloride or to any of the excipients
- Any type of acute metabolic acidosis (such as lactic acidosis, diabetic ketoacidosis)
- Diabetic pre-coma
- Severe renal failure (eGFR <30 mL/min)
- Acute conditions with the potential to alter renal function, such as dehydration, severe infection, shock
- Disease which may cause tissue hypoxia (especially acute disease, or worsening chronic disease) such as decompensated heart failure, respiratory failure, recent myocardial infarction, shock
- Hepatic insufficiency, acute alcohol intoxication, alcoholism

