## **Exclusion criteria**

Presence or history of any psychotic disorder is an exclusion for the ropinirole arm in this study.

Other exclusion criteria are as per SmPC:

- Hypersensitivity to the active substance or to any of the excipients
- Severe renal impairment (creatinine clearance\* <30ml/min) without regular haemodialysis
- Hepatic impairment

\* eGFR will be used to assess renal function in EXPERTS-ALS

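### The promised ranking of all drugs loses its randomised basis after a complete changeover of arms, and pairwise contrasts are not limited to patients eligible for both drugs

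*Protocol*

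**What the plan says.** **Ranking.** Primary objective 2 (protocol section 3.2) covers a drug's rank against both concurrent and earlier competitors. Section 11.1 adds that "we will then rank all candidate drugs by their effectiveness in decreasing NFL levels", using a Bayesian network meta-analysis described as keeping the concurrent randomised comparisons whole, with a probability that each drug is best or worst.

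**Arms.** Section 2.2 rules out a placebo arm by design. In the Figure 2 panel where no drug survives, three futile drugs leave and "Three new drugs are included". Section 4 presents the figures as illustrations that may change, and section 2.4 lets approved arms open one at a time or together. Under section 11.1 a first reference drug exists only after a drug has passed both futility analyses and met the effectiveness criterion with 80 patients per arm. It then keeps recruiting.

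**Allocation.** Section 7 states that "the participant will be randomly allocated to one of the current treatment options for which they are eligible" and that "A patient must be eligible for a minimum of two treatment arms". It also says "We will use probabilistic minimisation to balance site of onset (bulbar vs spinal) and groups of trial sites based on patient volume", so eligibility pattern is not a balancing factor. Exclusions differ by arm. Appendix 2 says "Pre-existing diabetes is an exclusion for the metformin arm in this study"; Appendix 5 also excludes diabetes from salbutamol. Appendix 4 says "Presence or history of any psychotic disorder is an exclusion for the ropinirole arm in this study". Hepatic impairment closes nifedipine and ropinirole, while doxycycline lists only hypersensitivity.

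**Contrasts.** Section 11.1 analyses all patients as randomised. For concurrently randomised drugs not declared futile, "we will estimate pairwise between-group mean differences in NFL levels at 18 to 24 weeks with 95% credible intervals". Section 11.2 sets 80 per arm for more than 80% power with a 0.10 log10 margin or difference.

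**The concern.** There are two gaps between the randomisation and the comparisons built on it.

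The first concerns the network. A network meta-analysis compares two drugs on randomised evidence only if a chain of concurrent randomisations joins them. If every arm closes before any new arm opens, no patient has been randomised across the boundary. Ranking drugs on both sides of it then needs something other than concurrent randomised comparisons, which is not what section 11.1 promises. What is at stake is primary objective 2.

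The second concerns eligibility. Concurrency deals with calendar time. It does not deal with patients in one arm who could not have been allocated to the other. If those patients enter a contrast, part of it compares different kinds of patient, selected by comorbidity or co-medication. Adjustment for baseline NFL may reduce the resulting bias but does not restore randomisation. What is at stake is the randomised status of the non-inferiority and superiority contrasts.

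**Working it through.** **Stated pairwise power.** Inputs from section 11.2: SD 0.35 log10, 80 per arm, margin or difference 0.10. The correlation of 0.80 is stated there for the futility analyses and is assumed here for the pairwise analysis. The error level is one-sided 0.025, matching the 2.5% posterior threshold.

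- Change score: SD = 0.35 × √(2 × (1 − 0.80)) = 0.2214. SE of the difference = 0.2214 × √(2/80) = 0.035. Power = Φ(0.10/0.035 − 1.96) = 81.5%; 77 per arm are needed for 80%.
- Baseline-adjusted: SD = 0.35 × √(1 − 0.80²) = 0.210, giving 85.4%; 70 per arm are needed.
- Averaging two baseline and two follow-up values, with correlation 0.80 between every pair: about 98%; 37 to 39 per arm are needed.

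All three agree with the stated figure of more than 80%.

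**Eligibility mixing.** The document gives no ineligible share, so it is assumed. Let a fraction f be ineligible for A only, with three arms and equal allocation among the arms open to each patient. The share of arm B that could never have received A is (f/2) / ((1 − f)/3 + f/2).

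- f = 10%: 0.05 / (0.30 + 0.05) = 14.3%
- f = 20%: 0.10 / (0.267 + 0.10) = 27.3%
- f = 30%: 0.15 / (0.233 + 0.15) = 39.1%

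The corresponding share in arm A is zero. With the five current arms and an assumed 10% with diabetes, who are barred from metformin and salbutamol, the doxycycline arm would hold (0.10/3) / (0.90/5 + 0.10/3) = 15.6% with diabetes, against none on metformin.

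The shift in the contrast is this share times the difference in mean NFL change between the two kinds of patient. That difference is also unknown. Assuming 0.05 to 0.15 log10, the shift is 0.007 to 0.021 at f = 10% and 0.020 to 0.059 at f = 30%.

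**Power after restriction to co-eligible patients.** With 80 randomised per arm and the same co-eligible share in both arms:

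| Co-eligible share | n per arm | Change score | Baseline-adjusted |
|---|---|---|---|
| 100% | 80 | 81.5% | 85.4% |
| 90% | 72 | 77.4% | 81.5% |
| 80% | 64 | 72.4% | 76.8% |
| 70% | 56 | 66.7% | 71.2% |

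**Network break.** Section 11.2 plans for 700 participants and 9 to 20 drugs, depending on how many are retained. 700/80 = 8.75, about 9. 700/35 = 20, where 35 is the approximate number randomised per arm at futility analysis 2. The upper planning figure therefore matches a trial in which no arm goes on to 80 and no reference drug is ever set.

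For three truly inert drugs with independent results, the stated futility figures (above 80% at analysis 1, above 90% at analysis 2) give a chance that all are dropped of at least about 0.80³ = 51% and 0.90³ = 73%. For five inert drugs the values are 0.80⁵ = 33% and 0.90⁵ = 59%.

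**The case against.** **On the network.** Figure 2 is labelled illustrative, arms may open singly, and the management group decides whether to drop an arm. A retained drug or staggered openings would keep a link. All of this is right, and it makes the break conditional. It does not remove the conflict, because nothing requires overlap and no fallback for the ranking is stated.

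A reader might infer that the break also undermines the non-inferiority and superiority tests. It does not: section 11.1 confines them to concurrent arms and leaves out drugs dropped for futility. A reader might also take 51% to 73% as the probability of a break. Those figures assume three inert drugs with independent results, and a break further requires that nothing new opens before the last arm closes. Nor do the documents show that cross-cycle ranks would come from the prior; the model for that case is not described.

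**On eligibility.** A reader might infer that patients ineligible for the comparator are definitely included. The text does not say so. Section 11.1 leaves further detail to the SAP, which is not shown, and a co-eligible set would be compatible with its wording. What stands is that the only limits the protocol places on contrasts are concurrency and analysis as randomised.

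Not every exclusion creates imbalance: diabetes closes both metformin and salbutamol, so it does not distort that pair. The associations cited in the appendices concern ALS incidence or risk, not NFL change in people who already have ALS. Section 2.1 describes individual NFL as fairly constant over time, and baseline NFL is in the model; both argue for modest subgroup differences. An assumed difference of 0.15 would equal the drug effect the futility analyses are powered to detect.

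**Conclusion.** The point holds in two limited parts, and both should be settled before the first pairwise analysis or ranking.

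1. After a complete changeover of the kind Figure 2 illustrates, with no placebo and no retained drug, the protocol cannot both rank every candidate drug and rest that ranking wholly on concurrent randomised comparisons. This is conditional on there being no overlap between old and new arms. It affects primary objective 2, specifically how drugs from a wholly dropped cycle rank against later ones.

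2. As written, pairwise contrasts are not restricted to patients eligible for both drugs, although allocation is. The 14% in the three-arm example depends on the assumed 10% ineligible share. The documents give no basis for the size or direction of any bias, so the shifts of 0.007 to 0.059 log10 only illustrate the assumptions.

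**What to change.** **Contrasts.** For each pairwise contrast and each network edge, include only participants recorded at randomisation as eligible for both drugs while both were open. Section 7 already requires the investigator to indicate the eligible arms before allocation, so no new data are needed.

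Keep 80 randomised per arm and restate the pairwise power for the co-eligible number. The cost is power, as tabulated above. It is small if the repeated baseline and follow-up values give the precision of the averaged model, since 37 to 39 co-eligible patients per arm would then suffice. Holding 80% power on a single change score would instead take about 77/0.90 = 86, 77/0.80 = 97 or 77/0.70 = 110 randomised per arm at 90%, 80% or 70% co-eligible. That is a sample-size increase and not a wording change, and each pair would have its own co-eligible set.

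**Ranking.** Rank drugs, and give the probability of being best or worst, only within sets joined by concurrent randomisation. Across unlinked sets, show the arm-specific changes from baseline that section 11.1 already plans for every drug, side by side and labelled as non-randomised. Qualify primary objective 2 to match. The cost is that there is no single league table if cycles are unlinked.

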### 8. Outcomes

#### 8.1 Primary outcome/endpoint

Change in blood NFL levels from baseline to weeks 18 and 24.

#### 8.2 Secondary outcomes/endpoints

- Change in ALSFRS-R score from baseline to weeks 12 and 24
- Progression in King's Stage from baseline to week 24 by 1 stage or more
- Adverse events and serious adverse events during the trial (definitions in Section 10).

#### 8.3 Exploratory outcomes/endpoints

- Survival at 12 months without non-invasive ventilation >22 hr/day or invasive ventilation, compared with the ENCALS median prediction of survival without non-invasive ventilation >22 hr/day or invasive ventilation (16,17).
- Change in WHO Disability Assessment Schedule (WHODAS 2.0) and Quality of Life (WHOQOL-Bref) at 24 weeks (or early discontinuation of treatment) against a natural history cohort.
- In-person forced vital capacity (FVC) and peak cough flow (PCF), compared with remote FVC (rFVC) and remote PCF (rPCF) where readings are available within +/- 7 days of each other.

#### 8.4 Feasibility outcomes

The trial will include an internal pilot. After approximately 8 months of start of recruitment, Sheffield CTRU will aggregate study data to assess the feasibility of the research based on the following feasibility outcomes:

## Table 1: Feasibility outcomes

Outcome	Red*	Amber**	Green***
Site set up (number of centres set up	<6 centres (<50%)	6-10 centres	11 centres
and recruited their first participant)		(50-91%)	(100%)
Participant recruitment	<60%	60-99%	100%
Proportion of NFL results (primary	<80%	80-90%	>90%
outcome) useable/verified			

\* Trial may be stopped if adaptations deemed unlikely to result in necessary improvement

\*\* Trial proceeds but adaptations may be required

\*\*\*Trial proceeds

## 9. Assessments and procedures

#### Figure 3. EXPERTS-ALS flowchart.

## 9.1 Study assessments schedule

Table 2: Study Assessments Table

Assessments	Week -2	Week 0 a (Baseline)	Week 4 b	Week 8 b	Week 12	Week 18	Week 24	EDoT visit c	Month 12
Visit window	-/+ 1 wk		+/- 1 wk	+/- 1 wk	+/- 1 wk	+/- 1 wk	+/- 1 wk		+/- 1 wk
Informed consent	Х								
Eligibility review d	Х	Х							
Demographics d	Х								
Socioeconomic status d	Х								
Brief health literacy screening	Х								
tool									
Medical history d	Х								
Pregnancy test e		Х					Х	Х	
NFL sampling	Х	Х			Х	Х	Х		
Safety bloods f	Х								
Weight	Х				Х		Х		
Vital signs	Х								
Physical examination	Х								
ECG p	Х								
Other IMP-specific monitoring g			Х	Х	Х	Х	Х	Х	
ALSFRS-R	Х	Х		Х	Х	Х	Х		
King's Stage	Х	Х					Х		
FVC	Х	Х			Х		Х		
Remote FVC h	X i	X i,j	X k	Х	Х	Х	Xj		
Peak cough flow	Х	Х			Х		Х		
Remote peak cough flow h	X i	X i,j	X k	Х	Х	Х	Xj		
ECAS	Х								
Randomisation		Х							
WHODAS 2.0		Х					Х	Х	

Assessments	Week -2	Week 0 a (Baseline)	Week 4 b	Week 8 b	Week 12	Week 18	Week 24	EDoT visit c	Month 12
Visit window	-/+ 1 wk		+/- 1 wk	+/- 1 wk	+/- 1 wk	+/- 1 wk	+/- 1 wk		+/- 1 wk
WHOQOL-BREF		Х					Х	Х	
Dispense study drug		Х	Х	Х	Х	Х			
Drug accountability			Х	Х	Х	Х	Х	Х	
Study medication administration		Continually recorded							
Concomitant medications	Continual	Continually recorded							
Adverse events	Continual	Continually monitored and documented							
Serious adverse events	Continual	Continually monitored and documented							
Survival data		Continually recorded						Х	
Sample collection for future r	research								
Blood sample		XI			XI		Х	Х	
Urine sample		Х			Х		Х		
Stool sample q		Х			Х		Х	Х	
Data collection for future res	earch								
Lifestyle questionnaire		Х			Х		Х	Х	
Food diary m,o,q		Х			Х		Х	Х	
FVC PDF reports n, o	Х	Х			Х	Х	Х	Х	

- a. Refer to IMP specific appendices for drug titration requirements. Note that additional remote contact (for example, telephone calls) and/or visits may be required in order to complete the drug titration.
- b. Week 4 and week 8 visits may be completed remotely unless there are IMP specific monitoring requirements as detailed in the IMP specific appendices. Study drug dispensing and accountability are not required for remote visits.
- c. An early discontinuation of treatment (EDoT) visit should be completed for participants stopping study treatment early. This may be completed at the same time as another scheduled visit or as a separate visit at the discretion of the local investigator. If a participant stops study treatment early but remains in the study for follow-up, the following assessments do not need to be repeated at week 24 if they are completed at EDoT: pregnancy test, WHODAS 2.0 and WHOQOL-BREF.
- d. Refer to section 5.5 for details.

- e. Persons of childbearing potential must have a negative pregnancy test prior to randomisation (at the baseline visit or within 7 days prior to baseline) and at treatment discontinuation or at the next study visit (see Section 5.8 for definitions). Additional testing may be required for individual IMPs, refer to the IMP specific appendices for details.
- f. As per section 9.6 the following parameters will be measured: Full blood count including haemoglobin, white blood count, lymphocytes, neutrophils and platelets; liver function tests including ALT, AST, ALP, bilirubin and GGT; renal function tests including sodium, potassium and eGFR.
- g. Determined by IMP under investigation refer to the IMP-specific appendix for details.
- h. Test can be completed +/- 7 days around appointment date.
- i. Face-to-face training provided for participants at screening and baseline visits.
- j. Conducted at same time as standard FVC/peak cough flow.
- k. Remote training provided for participants at week 4.
- I. An overnight fasting period is required for the blood samples collected at the baseline and week 12 visits.
- m. A food diary will be completed by the participant over the three days leading up to the stool sample collection. The local study team will record in the database whether the diary has been completed or not but the data will not be entered into the trial database. Paper copies of the diary will be stored securely by the participating site.
- n. The study team will download PDF reports from home spirometers at each study visit where possible, the procedure is detailed with the FVC / PCF procedure document. The local study team will record in the database whether the reports have been downloaded but, other than FVC and peak flow values recorded within the app, the data will not be entered into the trial database. PDF copies of the reports will be stored securely by the participating site prior to being securely transferred to the University of Sheffield for analysis.
- o. Non-database items.
- p. ECG only required if salbutamol is a potential outcome of randomisation.
- q. Stool sample kits and food diaries to be given to participants at screening, baseline and week 12.

